7. STUDY SCHEDULE

Visits will be broken up as the participant wishes. The 3-month follow up assessments should be carried out within 2 weeks of completing the intervention, or standard care period where possible.

It is expected that each participant will partake in the study for 10-months in total. 3-months is the end of the intervention period, 6- and 9-months are follow-up.

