10.2 Reporting procedures for Adverse Events

Common non-life-threatening symptoms such as constipation, diarrhoea, colds, headache, etc. do not need to be reported for this study. Only adverse events **causally related** to the study procedures will be recorded and captured on the Adverse Events log within the participants' CRF. The following information will be recorded: description, date of onset and end date, severity, assessment of relatedness to study, other suspect device and action taken. Follow-up information should be provided as necessary. The relationship of AEs to the study will be assessed and signed off by a medically qualified individual who has been delegated the duty on the study Delegation of Authority and Signature Log.

AEs considered related to the study will be followed until resolution or the event is considered stable. All related AEs that result in a participant's withdrawal from the study or are present at the end of the study, will be followed up until a satisfactory resolution occurs.

It will be left to the investigator's clinical judgment whether or not an AE is of sufficient severity to require the participant's removal from treatment. A participant may also voluntarily withdraw from treatment due to what they perceive as an intolerable AE. If either of these occurs, the participant must undergo an end of study assessment and be given appropriate care under medical supervision until symptoms cease or the condition becomes stable.

The severity of events will be assessed on the following scale: 1 = mild, 2 = moderate, 3 = severe.

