All other SAEs will be recorded using the SAE Log CRF. SAE data will be recorded on the REDCap database at regular intervals so that the LCTU can generate up-to-date reports for DSMC meetings. The DSMC will review the listings for clinical relevance and advise the TSC and Sponsor on the suitability of the continuance of the study following their review of the ongoing safety data and whether any further data should be collected or additional analyses undertaken.

Deaths will be recorded as part of the study outcomes and therefore will not be subject to expedited reporting.

SAEs will be reported using appropriate forms and according to the Sponsor SOP for reporting serious adverse events. Additional information will be provided if requested to the Sponsor and main Research Ethics Committee (REC). The Principal Investigator or another delegated physician (as agreed by the Sponsor) is responsible for the review and sign off of the SAE and the assessment of causality (i.e. whether an event is related to a study procedure or intervention).

The Sponsor will perform an initial check of the information and ensure that the SAE line listing is reviewed by the Director of Research & Innovation. All SAE information must be recorded on an SAE form and sent

to the Sponsor. Additional information received for a case (follow-up or corrections to the original case) needs to be detailed on a new SAE form and sent to the Sponsor.

Copies of all documentation and correspondence relating to SAEs will be stored in the TMF and/or ISF. Any change of condition or other follow-up information should be emailed to the Sponsor as soon as it is available or at least within 24 hours of the information becoming available. Events will be followed up until the event has resolved or a final outcome has been reached.

All SAEs will be tabulated and summarised by treatment group, according to system organ class and preferred term, as classified in the Medical Dictionary for Regulatory Activities (MedDRA). No formal statistical testing will be performed. All events will be summarised by seriousness, expectedness and relatedness.

The Sponsor will report all SUSARs to the Research Ethics Committee concerned. Fatal or life-threatening SUSARs must be reported within 7 days and all other SUSARs within 15 days. The CI will inform all investigators concerned of relevant information about SUSARs that could adversely affect the safety of participants.

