11.3.2 Descriptive analysis

Data will be checked for outliers and missing values and validated using the defined score ranges for all outcome measures. Baseline data will be summarised by group to assess comparability between treatment arms, and to highlight any characteristic differences. Statistical tests for imbalance will not be carried out.

It is likely that some data may not be available due to death, kidney transplantation, and voluntary withdrawal of participants or lack of completion of individual data items. Where possible the reasons for missing data will be ascertained and reported. Although every effort will be made to minimise crossovers from both intervention arms, the numbers, direction and reasons for participants moving between arms will be recorded and reported in line with CONSORT (Consolidated Standards of Reporting Trials) guidance.

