11.3.4 Analyses of secondary outcomes

The secondary outcomes will be analysed in a similar manner to the primary outcome. All represent continuous data and therefore linear regression will be used. All analyses will be adjusted for baseline value and the stratification factors. The number of deaths and cardiovascular events expected is relatively low, therefore formal time to event analyses will not be conducted. Kaplan–Meier will be presented to describe the relationship between these events and treatment.

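### If cardiovascular events are plotted alone by Kaplan-Meier, as section 11.3.4 reads most plainly, the curve slightly overstates the proportion affected; cumulative incidence would avoid this at almost no cost.

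*Protocol*

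**What the plan says.** All references are to the main STIM-HD randomised trial protocol.

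- Section 11.3.4 (Analyses of secondary outcomes): "The number of deaths and cardiovascular events expected is relatively low, therefore formal time to event analyses will not be conducted". It continues: "Kaplan–Meier will be presented to describe the relationship between these events and treatment". It defines no composite, gives no censoring rule for death, and does not say whether the two event types share a curve. No cumulative-incidence or competing-risk method is named anywhere in the protocol.
- Section 11.3.2 (Descriptive analysis) foresees deaths: "It is likely that some data may not be available due to death, kidney transplantation, and voluntary withdrawal of participants".
- Section 10.3 (Reporting Procedures for Serious Adverse Events): "Deaths will be recorded as part of the study outcomes". The same section has serious adverse events tabulated by treatment group, by system organ class and preferred term.
- Section 7 (Study schedule) sets the horizon: "3-months is the end of the intervention period, 6- and 9-months are follow-up".

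**The concern.** Someone who dies without having had a cardiovascular event can no longer have one. A Kaplan-Meier curve for cardiovascular events alone cannot represent that. It censors the death, which treats the person as if they stayed at risk. One minus Kaplan-Meier then estimates the proportion who would have an event if nobody died first, and this exceeds the proportion who do have one as soon as a single such death occurs.

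Readers commonly take such a curve as absolute risk. On that reading each arm's figure would be somewhat too high. If deaths differed between arms, the two figures would be raised by different amounts. What is at stake is the accuracy of one descriptive figure. No test or listed endpoint is involved.

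**Working it through.** **Inputs from the protocol.** Follow-up is 9 months after randomisation (section 7), with 114 participants per arm (section 11.1). The protocol states no risk of death or of cardiovascular events, so it has no figure of its own to reproduce here.

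**Assumptions.** Each event has a 9-month risk between 3% and 15%, where each risk is what would be seen if the other event did not occur. Hazards are constant. Death here means death without a prior cardiovascular event.

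**Formulas**, with c the cardiovascular risk and d the risk of death:
- Cumulative hazards over 9 months: Hc = −ln(1 − c) and Hd = −ln(1 − d).
- One minus Kaplan-Meier, deaths censored: 1 − exp(−Hc) = c.
- Actual cumulative incidence: Hc/(Hc + Hd) × [1 − exp(−(Hc + Hd))].

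**Worked case, c = d = 10%.** Hc = Hd = 0.1054, so the first factor is 0.5. The second is 1 − 0.90 × 0.90 = 0.19. Cumulative incidence is 0.5 × 0.19 = 9.50%, against 10.00% from Kaplan-Meier. The excess is 0.50 points, and 114 × 0.0050 = 0.57 patients.

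| c | d | 1 − KM | Cumulative incidence | Excess (points) | Patients per 114 |
|---|---|---|---|---|---|
| 3% | 3% | 3.00% | 2.96% | 0.05 | 0.05 |
| 5% | 5% | 5.00% | 4.88% | 0.13 | 0.14 |
| 10% | 5% | 10.00% | 9.75% | 0.25 | 0.28 |
| 10% | 10% | 10.00% | 9.50% | 0.50 | 0.57 |
| 15% | 10% | 15.00% | 14.26% | 0.74 | 0.85 |
| 15% | 15% | 15.00% | 13.88% | 1.12 | 1.28 |

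In relative terms the excess is about 1.5% when d = 3% and about 8% when d = 15%.

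**Between arms.** Give both arms the same cardiovascular hazard, with d = 5% in one and 15% in the other. The two Kaplan-Meier curves coincide. The cumulative incidences differ by 0.26 points at c = 5%, 0.51 at c = 10% and 0.76 at c = 15% (14.63% against 13.88%). The arm with more deaths has the lower figure.

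**Against sampling error.** For a 10% proportion in 114 people, the 95% half-width is 1.96 × √(0.10 × 0.90/114) = 5.5 points, about 11 times the 0.50-point excess above. For a difference between two arms at 15%, it is 1.96 × √(2 × 0.15 × 0.85/114) = 9.3 points, against a shift of at most 0.76.

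**The case against.** The strongest reply is that the fault is inferred. Section 11.3.4 does not say that deaths will be censored, that cardiovascular events will be plotted apart from deaths, or that one minus Kaplan-Meier will be read as absolute risk. The two event types could be meant as a composite, for which Kaplan-Meier raises no problem of competing deaths. This stands in part. Censoring follows from the method only if the events are plotted alone. That is the plainer reading, since two event types are named and no composite is defined, but it is not the only one.

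A second reply is that section 11.3 leaves full analysis details to the statistical analysis plan. That covers the event definition and the curve's data source, and neither is raised here as an omission. It does not cover the method itself, which the protocol has already named.

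A third reply is size. The protocol expects few events, the plot is untested, and the excess is far below sampling error. This stands, and it is why the point is minor.

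Three stronger readings are tempting but not supported:
- **That Kaplan-Meier misrepresents the comparison between arms.** With equal cardiovascular hazards it correctly shows equal curves. Kaplan-Meier tracks the cause-specific hazard and cumulative incidence tracks absolute risk, so the contrast is one of estimand.
- **That these curves are the only description of cardiovascular events by arm.** Section 10.3 also tabulates serious adverse events by treatment group, and those crude counts carry no such inflation.
- **That the curve can hold only serious events from the serious adverse event log.** Under section 10.2 only events causally related "to the study procedures will be recorded and captured on the Adverse Events log", so unrelated non-serious events would not arrive by that route. However, sections 7.1 and 7.2 list capture of routine clinical data, and section 8.13.1 draws on patient-reported admissions and the UK Renal Registry. The protocol does not say whether these feed the plot.

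**Conclusion.** The point holds as a minor one. Kaplan-Meier is the right display for all-cause death. For cardiovascular events plotted alone it overstates the absolute proportion affected, always in the same direction, by about 0.05 to 1.1 percentage points per arm over 9 months. Deaths of 5% against 15% would shift the between-arm difference in absolute risk by at most about 0.8 points.

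These sizes rest on assumed risks of 3% to 15% and constant hazards, because the documents give no rates. The direction needs only that cardiovascular events are plotted separately and that someone dies without a prior event. If a composite with death was intended, the problem disappears and only the wording needs attention.

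**What to change.** In section 11.3.4:
- Keep Kaplan-Meier for all-cause death.
- For cardiovascular events, present the Aalen-Johansen cumulative incidence by arm, with death without a prior cardiovascular event as the competing event. If a composite was meant, state that Kaplan-Meier will be shown for death or first cardiovascular event.

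The cost is one sentence and a standard software routine. No new data should be needed, because the planned curves already require dates of death and of cardiovascular events.

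There is one small drawback. Cumulative incidence can look lower in an arm simply because more people died there first. It should therefore be shown beside the mortality curve.

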11.4. Subgroup analyses

A priori sub group analysis will include, gender, age, time on dialysis, physical activity levels (i.e. sedentary versus active) and the severity of sarcopenia at baseline (i.e. probable vs severe).

11.5 Adjusted analyses

The primary analysis will be adjusted for the minimisation factors.

11.6 Interim analysis and criteria for the premature termination of the study

No criteria for early termination of the study have been set.

11.7 Participant population

We will recruit haemodialysis patients (either home or unit based) who have been receiving dialysis for more than 3 months.

11.8 Procedure(s) to account for missing or spurious data

By design there will be no missing data for the minimisation factors, if the primary outcome is missing for less than 5% of the study population at baseline and 3-months, a complete case analysis will be conducted. If there is more than 5% missing outcome data, multiple imputation will be used. The imputation will be carried out using the command MI in Stata. MI replaces missing values with multiple sets of simulated values to complete the data, performs standard analysis on each completed dataset, and adjusts the obtained parameter estimates for missing-data uncertainty using Rubin's rules to combine estimates.

12. DATA MANAGEMENT

12.1 Data Flow Diagram

This is a separate PDF document.

12.2 Data collection tools and source document identification

All physical function data will be entered into an electronic case report form (REDCap) and collated on an excel spreadsheet. All pseudonymised lab data will be collated and stored using the lab archives online database as well as in individuals' lab books. These lab books contain pseudonymised results of the experiments performed with the biological samples, the methods used and any variation of these methods and will be used throughout the study.

12.3 Source Data

Source documents collected during this study include, clinical records, completed questionnaires, and ultrasound scans. In addition, all physiological data will be entered into an electronic case report form and will also be considered as source data.

All documents will be stored safely in confidential conditions. On all study-specific documents, other than the signed consent, the participant will be referred to by the study participant number/code, not by name.

12.4 Data handling and record keeping

Each participant will be assigned a unique identification number upon consent and this will be added to all study documents/data collection tools in place of the participant's name. All study data will be entered on to paper CRFs before being entered into the REDCap database. The database will be located on a University of Leicester server.

A copy of the completed participant informed consent form and participant information sheet will be placed in the medical notes of all participants and in the Investigator Site File. A sticker will be placed on the cover of the notes (or inside cover) detailing the study title, contact details of the PI and the fact that the notes should not be destroyed for 6 years from the end of the study. All study visits summaries and relevant SAEs will be recorded in the hospital notes.

A contacts database (containing participant contact details) will be held separately from the study database. Participants' contact details will be held securely in accordance with data protection regulations. This will be password protected and managed by the research team at each site.

All data handling and record keeping will be kept in adherence to University of Leicester's and relevant NHS Organisations' policies. All study documentation containing identifiable patient data will be managed in accordance with ICH-GCP, The UK Policy for Health and Social Care Research and the Data Protection Act.

12.5 Access to Data

Direct access will be granted to authorised representatives from the Sponsor, host institution and the regulatory authorities to permit study-related monitoring, audits and inspections in line with participant consent.

The Chief Investigator and relevant study staff will have access to the data collected as part of this research. Access to the study database will be restricted by role-based permission to authorised study personnel will be suitably trained on the system prior to being granted access. Individual user accounts will be password-protected and will not be shared between members of the study team.

12.6 Archiving

Research data and archived files will be stored for a minimum of 6 years after the study has ended. Storage will comply with the University of Leicester archiving Standard Operating Procedure. Details can be found at: https://le.ac.uk/research/regi/standard-operating-procedures. Destruction of essential documents will require authorisation from the Sponsor. Archiving of source data or the Investigator Site File (ISF) for participating sites will be arranged by the relevant participating site.

13. MONITORING, AUDIT & INSPECTION

The University of Leicester as Sponsor operates a risk-based monitoring programme with this study will be subject to.

14. ETHICAL AND REGULATORY CONSIDERATIONS

14.1 Research Ethics Committee (REC) review and reports

Once the initial sponsor review process is complete and a sponsor reference number has been allocated, and all requested documentation has been received and checked, authorisation from the University of Leicester's Research Governance Office will be issued to book further review of the proposed research. The University of Leicester's Ethics Committee or NHS Research Ethics Committee and the Health Research Authority will then review the proposal. Agreement in principle is subject to the research receiving all relevant regulatory permissions. Submission for regulatory approvals will be submitted via Integrated Research Application System (IRAS). The Chief Investigator will ensure that all regulatory approvals, confirmation of capacity and capability from NHS sites and sponsor greenlight are in place before participants are approached.

For any required amendments to the study, these will be submitted to the sponsor in the first instance for review and approval to submit the amendment for external regulatory approval. Amendments must be implemented following all required ethical, site and Sponsor approvals and in line with Sponsor Standard Operating Procedures. The Research Governance Office's Standard operational procedures will be followed for the duration of the study.

The Chief Investigator will notify the REC when the study has ended by completing the end of study notification form and will submit a final report of the results within one year after notifying REC.

A Trial Master File will be maintained for the duration of the study and will be stored for 6 years after the study has ended. The only time this could be exceeded, is if samples are being retained beyond the scope of the original study i.e. there is consent for future research. In this circumstance ICFs would have to be retained for as long as the samples are in existence, as we have a legal requirement to prove the samples were obtained with consent.

14.2 Peer review

Prior to review by the sponsor, the protocol has been through the external peer review as part of the grant submission process. It was externally reviewed by seven experts.

14.3 Public and Patient Involvement

Population (P): As part of other NIHR funded research within the dialysis population, we have established a national Patient Participation, Involvement and Experience (PPIE) group comprising people on dialysis and their family / carers. This group, led by our patient co-applicant ([name]) have helped co-develop the research question and study design both for the stage 1 application and subsequently for this stage 2 research plan.

Research question and intervention (I): The PPIE group understood the benefits of regular exercise, but despite motivation and intention, many are unable to exercise consistently. They felt NMES might be a more realistic therapy they would be able to take part in on a regular basis. Reviewing the intervention, a number of improvements were made to the protocol:

- Inclusion (and design) of the external pilot study to assess the tolerability (Work package 1)
- To include issues of comfort (including the pad size and their placement)
- Inclusion of an adapted screening phase to allow potential participants to trial the NMES intervention before consent (and minimise attrition / drop out).
- Input into the randomisation technique (individual vs cluster) for work package 2 and then insight into mitigation strategies to prevent contamination between groups (use of curtains, additional time discussing in clinic rooms) and their acceptability to participants.
- To broaden the eligibility criteria to include home haemodialysis patients and ways to ensure participation is least intrusive to encourage enrolment.

Control (C): All patients were keen to be able to try NMES if they were in the study. However, the PPIE group provided reassurance that patients randomised to standard care would understand the importance of the randomised design (and the 50% chance of being allocated to the control group), minimising the impact of resentful demoralisation. Nevertheless, there was a clear message to ensure that the NMES device was affordable and easy to use as participants may wish to purchase their own after the study (irrespective of group allocation). This has been updated to ensure a commercially available device is used throughout.

Outcome (O): Patients highlighted muscle weakness (which makes up the principal component of the diagnosis of sarcopenia) as one of the most intrusive symptoms they experience. Following feedback from the Funding Committee, the PPIE group were pleased to include additional measures of quality of life (KDQoL) as well as symptom burden (fatigue) that are known to be some of the most important outcomes to people on dialysis. The 6-month extension to the protocol to allow for this additional data collection was seen as a positive step and as with previous studies. There was no anxiety around questionnaire fatigue because the participants are attending for their treatment at that time, in any case. To ensure that the intervention is as easy to undertake by home haemodialysis patients in the community and that the outcome measures are as straightforward to collect, a number of action points were highlighted by the PPIE members:

- To ensure a systematic approach is adopted for screening that ensures people on home haemodialysis are identified
- To allow as much flexibility as possible for scheduling visits at the pre-screening and consent stage (e.g. being able to travel to the nearest dialysis unit rather than hospital centre)
- To offer easy access to remote support and regular scheduled 'check-ins' to help ensure adherence to the intervention.

